**Table 4: Types of Analyses and Corresponding Populations for Planned Primary Analysis and NDA Analysis for FL**

Planned Analysis	Type of Analysis	Population	Analysis Set / Group
Primary Analysis for FL	Baseline disposition and demographics	ITT IS FL	ITT IS FL Total
	Primary endpoint ORR	PEP FL 	PEP FL
	Secondary endpoint DOR	PEP FL	DOR Primary Analysis Set for FL
	Selected Critical Secondary endpoints (PFS, OS)	PEP FL	PEP FL
	Selected Safety endpoints	Safety IS FL population	Safety IS FL Total
NDA Analysis for FL	Baseline disposition and demographics	ITT FL	PEP FL, ITT IS FL, ITT CS, ITT FL Total
	Primary endpoint ORR (Primary Analysis) and all secondary endpoints	PEP FL 	PEP FL
	Primary endpoint ORR (Supportive Analysis)	PEP FL 	PEP FL
	Primary endpoint ORR (Supportive Analysis)	ITT FL 	PEP FL, ITT IS FL, ITT CS, ITT FL Total
	Secondary endpoint DOR (Primary Analysis)	PEP FL	DOR Primary Analysis Set for FL
	Secondary endpoint DOR (Supportive Analysis)	ITT IS FL	DOR Supportive Analysis Set for FL
	Selected critical efficacy endpoints (PFS, OS, etc.)	ITT FL	PEP FL, ITT IS FL, ITT CS, ITT FL Total
Safety endpoints	Safety population	IS FL, IS MZL  , IS Total, CS	
Primary Analysis and NDA Analysis for MZL	Baseline disposition and demographics	ITT MZL	ITT MZL
	Primary endpoint ORR and all secondary endpoints (except DOR)	ITT MZL	ITT MZL
	Secondary endpoint DOR	ITT MZL	DOR Analysis Set for MZL
	Safety endpoints	Safety population	IS FL, IS MZL, IS Total, CS

 Primary analysis for ORR will include best response of PR and/or CR prior to first PD that is reported before the data cutoff date for FL Primary Analysis, among all patients in the Primary Efficacy Population in FL (PEP FL).

 Supportive analysis for ORR will include PR or CR achieved that is reported before the data cutoff date for NDA Analysis for FL, among all patients in the Primary Efficacy Population in FL.

 Supportive analysis for ORR will include PR or CR achieved that is reported before the data cutoff date for NDA Analysis for FL, among all patients in the ITT FL Population.

 Including MZL patients in the Safety Population who were dosed prior to the data cutoff date for the NDA Analysis for FL.

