### **3. ENDPOINTS**

#### **3.1. Primary Efficacy Endpoint**

The primary efficacy endpoint is ORR, defined as the proportion of subjects achieving the best response rating of CR or PR based on the Modified Lugano Classification (response criteria summarized in [Appendix 5](#) of Protocol Amendment 2), as determined by IRRC.

For both Primary Analysis and NDA Analysis for FL, ORR will include best response of PR and/or CR prior to first PD that is reported before the data cutoff date for FL Primary Analysis, among all patients in the Primary Efficacy Population in FL (PEP FL).

As supportive analyses for NDA Analysis for FL, ORR will be summarized by 1) including PR or CR achieved that is reported before the data cutoff date for NDA Analysis for FL, among all patients in the Primary Efficacy Population in FL; 2) including PR or CR achieved that is reported before the data cutoff date for NDA Analysis for FL, among all patients in the ITT FL Population.

Time to response will be assessed to provide supportive information for the primary endpoint of ORR. It is defined as the time from the first dose of study drug to the first objective response for the subjects who achieved best response of CR or PR.

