### **3.2.6. Recapture of Response**

Recapture of response is defined as achieving a second documented CR or PR after experiencing the first PD. The CT scan at PD will be used as new baseline for assessing disease response to ME-401.

Recapture of response rate (RRR) is defined as the proportion of subjects who achieved a CR or PR followed by a PD during IS dosing and subsequently switched to CS dosing and achieved a second documented CR or PR.

Time to recapture of response is defined as the time from the first PD until the second documented CR or PR. Subjects who do not have the second documented CR or PR will be censored at last time of response assessment.

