### **4.3. Efficacy Analysis Populations and Analysis Sets**

The primary efficacy population in FL (PEP FL) is defined as the initial 91 consecutive subjects enrolled in the ITT IS FL Population.

The DOR Primary Analysis Set for FL will include subjects in the PEP FL who achieved PR or CR prior to first PD, that is reported before the data cutoff date for the FL Primary Analysis.

The DOR Supportive Analysis Set for FL will include subjects in the ITT IS FL who achieved PR or CR prior to first PD, that is reported before the data cutoff date for the NDA Analysis for FL.

The DOR Analysis Set for MZL will include subjects in the ITT MZL FL who achieved PR or CR prior to first PD, that is reported before the data cutoff date for the MZL Primary Analysis.

The efficacy evaluable (EE) population will include all subjects who received at least one dose of study drug and had at least one response assessment post baseline.

Subjects will be analyzed by randomized group per Protocol Amendment 1 and by enrolled group (IS dosing) per Protocol Amendments 2 and 3. EE population will be used for selected efficacy analyses.

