## 7. EFFICACY ANALYSIS

### 7.1. Primary Efficacy Endpoint and Analysis

The primary efficacy endpoint is ORR, defined as the proportion of subjects achieving the best response rating of CR or PR based on the Modified Lugano Classification, assessed by IRRC.

For Primary Analysis and NDA Analysis for FL, ORR will be evaluated by summarizing the number and percentage of subjects with the best overall response (CR/PR) prior to first PD as assessed by IRRC that is reported before the data cutoff date for the Primary Analysis, along with 2-sided 95% exact Clopper-Pearson confidence interval (CI). The primary efficacy analysis will be based on the Primary Efficacy Population for FL (PEP FL).

As a supportive analysis for NDA Analysis for FL, ORR will be analyzed

- using the ITT FL Population by including the PEP FL, ITT IS FL, ITT CS, ITT FL Total patients
- by summarizing the number (percentage) of patients who achieved PR or CR before the data cutoff date for the NDA Analysis for FL submission.

As sensitivity analyses, the above analyses in [Section 7.1](#) will be repeated for EE population and PP population.

All subjects who did not meet the criteria for an objective response by the analysis cut-off date will be considered non-responders.

To evaluate the impact of the covid-19 pandemic on efficacy of ME-401, the above analyses in [Section 7.1](#) will also be conducted using the Modified ITT Population in IS FL patients, i.e., patients who discontinued from treatment early due to covid-19 deaths with no post-baseline efficacy assessment will be excluded from the analysis.

Subgroup analysis of ORR (the proportion of subjects with the best overall response [CR/PR] prior to first PD as assessed by IRRC), that is reported before the data cutoff date for the Primary Analysis, will be performed by the subgroups defined in [Section 5.5](#), based on PEP FL and ITT MZL population. Forest plots will be provided for ORR and 95% CI in selected subgroups.

Waterfall plots of maximum percentage decrease in sum of the products of longest diameters (SPD) measured by the IRRC will be provided for the patients in the PEP FL and ITT MZL population.

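### The supportive NDA ORR drops the limit to responses before first progression without saying so, and no row shows the before-progression ORR at that cutoff or in the full ITT IS FL population

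*SAP*

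**What the plan says.** **Primary ORR.** The first footnote to SAP Table 4 reads: "Primary analysis for ORR will include best response of PR and/or CR prior to first PD that is reported before the data cutoff date". The cutoff meant there is that of the earlier of the two FL analyses, and the population is the PEP FL. Sections 3.1 and 7.1 set the same rule.

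**Supportive ORR at the NDA analysis.** Footnotes 2 (PEP FL) and 3 (ITT FL, shown as PEP FL, ITT IS FL, ITT CS and total) read "Supportive analysis for ORR will include PR or CR achieved that is reported before the data cutoff date for NDA Analysis for FL". Section 3.1 describes both analyses as "including PR or CR achieved that is reported before the data cutoff date for NDA Analysis for FL". Section 7.1 counts those "who achieved PR or CR before the data cutoff date for the NDA Analysis for FL submission". None of the three places limits the count to responses before progression.

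**Supportive DOR at the same cutoff.** The set in Section 4.3 is "subjects in the ITT IS FL who achieved PR or CR prior to first PD", so the limit is kept. Section 3.2.2 agrees.

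**Supportive CR rate.** Section 3.2.3 limits the primary CR rate to CR before first progression. It then says openly that the supportive version counts CR at any time in the study for IS subjects who switch to CS. Section 7.2.3 ties the supportive version to the NDA cutoff.

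**Switching and recapture.** Section 2.3 lets subjects who progress on IS move to CS and asks for no earlier response. Membership of ITT IS FL, and so of the PEP FL, follows the intended regimen (Sections 4.2 and 4.3), so switchers stay in. Recapture of response (Sections 3.2.6 and 7.2.6) is restricted to subjects who had CR or PR before progression. Section 3.2.6 adds: "The CT scan at PD will be used as new baseline for assessing disease response to ME-401".

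**The concern.** A supportive ORR at a later cutoff, in the PEP and then in all IS subjects, is useful if it shows what longer follow-up and a wider population do to the response rate. Here the response rule changes as well. A first response reached on CS after failure on IS can be credited in rows named for the IS population, although Protocol Section 3 states the aim as evaluating the IS regimen. The recapture endpoint does not pick such a subject up, because it requires an earlier response, so the supportive ORR is where that subject would appear.

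At stake is how a secondary figure in the NDA package is read. If the supportive ORR exceeds the primary ORR, the reader cannot tell late responses on IS from first responses on CS.

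**Working it through.** **1. The rules side by side (SAP Table 4; Sections 3.1, 3.2.2, 4.3 and 7.1).**

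| Analysis | Population | Cutoff | Limited to before first progression? |
|---|---|---|---|
| Primary ORR | PEP FL | FL Primary Analysis | Yes |
| Supportive ORR, footnote 2 | PEP FL | NDA Analysis | No |
| Supportive ORR, footnote 3 | ITT FL, including an ITT IS FL column | NDA Analysis | No |
| Supportive DOR set | ITT IS FL | NDA Analysis | Yes |

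The table lacks an ORR limited to before first progression in the PEP FL at the NDA cutoff, and the same quantity in ITT IS FL.

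**2. Who is affected.**
- Response before progression: counted under either rule. A later recaptured response changes nothing.
- First response between the two cutoffs, without earlier progression: counted under either rule at the NDA cutoff. This is the genuine effect of follow-up.
- No response before progression, switch to CS, then CR or PR: counted only when the limit is absent.

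**3. Why the change cannot be attributed.** In the PEP FL,

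supportive ORR − primary ORR = (late first responses before progression + first responses after progression) / 91.

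Only the sum would be reported. In ITT IS FL the change of population is a third component.

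**4. Size.** The plan's own design figure comes first: N = 91, null 48%, alternative 65.5%, one-sided alpha 0.025 (SAP 2.4). In the exact binomial test the smallest passing count is 54/91 = 59.3%, with alpha 0.0196 and power 0.910. The stated power of at least 90% is reproduced, and this point leaves it untouched.

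Let k be the number of subjects whose first response comes after progression. The documents do not give k; 0 to 5 is an assumption.
- Shift in PEP ORR = k/91: k = 0, 0 points; k = 1, 1.1; k = 3, 3.3; k = 5, 5.5.
- For scale, the standard error of ORR at 65.5% is √(0.655 × 0.345 / 91) = 5.0 points.
- Illustration with 60/91 = 65.9% (exact 95% CI 55.3 to 75.5) before progression: k = 3 gives 63/91 = 69.2% (58.7 to 78.5); k = 5 gives 65/91 = 71.4% (61.0 to 80.4).
- In ITT IS FL, taking the planned 120 subjects: 1/120 = 0.8 points each, and 5/120 = 4.2 points for five.

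**5. The reference scan after a switch.** PR needs at least a 50% fall in SPD (Protocol Appendix 5, Table 7). If the scan at progression were the reference, PR would be reached at 0.5 × (SPD at progression). With SPD at progression assumed to be 1.5 times study baseline, that is 0.75 of baseline, a 25% reduction. At 2 times it is 1.0, no reduction. Whether the IRRC would read it this way is not settled:
- SAP 3.2.6 and Protocol 7.1 give the new reference in the context of recapture; Protocol 8.5 applies it to all who switch after progression.
- SAP 5.2.1 otherwise defines baseline as before first dose.
- SAP 7.2.6 has recapture assessed by both the IRRC and the investigator; Protocol 3.2 and 7.2.5 name the investigator only.

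**The case against.** The strongest reply is that the omission is intended. Section 3.2.3 uses the same pattern for CR and says so, and switching after progression is part of the protocol. A supportive ORR over the whole study is a legitimate summary of that strategy. This reply largely stands: the documents do not show a drafting error. It does not supply the missing label for ORR or the missing before-progression row.

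A second reply is that the before-progression ORR is not lost. The NDA analysis repeats the primary ORR in the PEP FL, and Section 7.1 repeats its analyses in the EE and PP populations and in a modified ITT population of IS FL patients. That is true, but the before-progression version keeps the Primary Analysis cutoff, and none of those populations is the full ITT IS FL.

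Readers might be tempted by stronger conclusions that the documents do not support:
- *That the DOR set proves the ORR wording wrong.* DOR runs to first progression, so a response after it cannot have a DOR. The DOR set needs the limit whatever the ORR rule is.
- *That the row can only raise ORR and so cannot test robustness.* In the PEP, a later cutoff alone also cannot lower a best-response rate, so the amended row would share that property. In the wider populations ORR can fall.
- *That re-baselined PRs certainly enter the IRRC endpoint.* The documents conflict on this, and the IRRC's methods are in a charter outside them.
- *That a failed comparison could be rescued.* Four added responses would take 50/91 (exact lower limit 44.2%) to 54/91 (48.5%), but the SAP specifies no test against 48% for the supportive ORR.

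**Conclusion.** The point holds as one of labelling and attribution. The supportive NDA ORR can include first responses reached after progression and a switch to CS, in rows named for the IS population. It does not say so, and Table 4 plans no row from which a reader could remove them. The primary ORR, its sample size and its comparison with 48% are unaffected.

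The effect is 1.1 points in the PEP FL per affected subject, or 0 to 5.5 points for an assumed 0 to 5 subjects. It may be nil: every IS subject has two cycles of daily dosing first (SAP 2.3), and in the Phase 1b study 48 of 54 responses were seen after the first two cycles (Protocol 1.6.2.4), so first responses on CS could be few. The case for acting rests on the low cost and the clearer reading, not on a demonstrated large bias.

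**What to change.** - In SAP 3.1 (supportive items 1 and 2), SAP 7.1 (second supportive bullet) and Table 4 (footnotes 2 and 3), define the supportive ORR for PEP FL and ITT IS FL as CR or PR *prior to first PD*, reported by the NDA cutoff.
- If the overall version is wanted, keep it beside that row, label it as including responses after switch to CS, and give first responses on CS a separate line, since recapture excludes them.
- Treat the supportive CR rate (SAP 3.2.3 and 7.2.3) the same way. Otherwise a first CR after a switch would count in supportive CR but not in supportive ORR.
- Reconcile SAP 3.2.6, 5.2.1 and 7.2.6 with Protocol 3.2, 7.1, 7.2.5 and 8.5 on which baseline scan the IRRC uses after a switch, and on whether the IRRC assesses those responses.

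The cost is SAP wording and one extra row, with no new data. The headline supportive ORR may be slightly lower.

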## 5.2. Key Definitions

### 5.2.1. Baseline

Unless otherwise specified, baseline is defined as the last non-missing assessment prior to the first dose date of study drug and within 28 days of first dose date. In cases where measurements are taken on the same day as the first dose of study drug and no times are reported, it will be assumed that these measurements are taken prior to study drug being administered therefore can be defined as baseline measurements.

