### **8.2. Screening Period**

Subjects will be screened during the 28-day period prior to Cycle 1 Day 1 to ensure they meet the entry criteria for the study. During the screening period, the Investigator should carefully review each subject's medical history to ensure eligibility. All inclusion and exclusion criteria should be supported by corresponding documentation in the medical records, including a pathology report confirming the diagnosis of FL or MZL.

The Investigator or an appropriate designee will obtain informed consent from each subject prior to conducting any study-specific procedures. Bone marrow biopsies performed as part of the subject's medical care within 12 weeks of Cycle 1 Day 1 may be used for screening and eligibility determination. PET/CT or CT scans performed within 6 weeks of Cycle 1 Day 1 may be used for screening and eligibility determination as long as they meet the minimum requirements per Lugano criteria (i.e., includes all appropriate anatomical areas of the body, a slice thickness  $\leq 5$  mm). This avoids unnecessary repeat tests and undue burden on subjects.

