- z. **Opportunistic Infection Monitoring** – Prior to start of every cycle of treatment with ME-401, monitoring will be conducted, and for subjects with identified risk factors and those who developed an OI while on study treatment, additional assessments should include: CD4 and CD8 count and ratio, c-reactive protein, blood cultures, any additional laboratory and diagnostic methods according to local SOC reported as unscheduled laboratory and diagnostic methods of assessment, radiological imaging (i.e., chest X-ray or CT scans). Note: Treatment of the OI that started while on study should be based on local SOC.
- aa. **Post-treatment Follow-up Procedures** – Every 3 months from the last dose of study drug to obtain data regarding changes in efficacy assessments, death or subsequent therapy based on standard of care assessments. Imaging tests to assess disease status will be performed at least once every 6 months or earlier as indicated per standard of care. Any AE that has not returned to baseline or Grade  $\leq 2$  should be followed until it has returned to baseline or better, the event is assessed as stable by the Investigator, the subject is lost to follow up, or the subject withdraws consent. Survival follow-up will continue for up to 3 years after the last subject is enrolled in the study.
- bb. **Response assessment** – Imaging scans, physical examination, bone marrow aspirate/biopsy (if applicable), and laboratory evaluation as appropriate for individual subjects.
- cc. **Response assessment at the EOT/30-Day Safety Follow-up visit** – Perform imaging test (CT scan or PET/CT scan) only if last imaging tests outside the window noted for CT scan or PET-CT.
- dd. **CT Scan** – CT of the neck, chest, abdomen, and pelvis must be obtained at screening (within 6 weeks prior to Cycle 1 Day 1). CT scans must be performed using IV contrast. For subjects who are intolerant to contrast agents, the CT scan will be performed with oral contrast or MRI scans will be used.
- ee. **PET/CT** – FDG-PET scan must be obtained at screening (within 6 weeks prior to Cycle 1 Day 1), as indicated, and to confirm CR/CMR. PET/CT imaging is no longer needed once a CMR has been achieved and a CT scan is an appropriate imaging test.

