- z. **Opportunistic Infection Monitoring** – Prior to start of every cycle of treatment with ME-401, monitoring will be conducted, and for subjects with identified risk factors and those who developed an OI while on study treatment, additional assessments should include: CD4 and CD8 count and ratio, c-reactive protein, blood cultures, any additional laboratory and diagnostic methods according to local SOC reported as unscheduled laboratory and diagnostic methods of assessment, radiological imaging (i.e., chest X-ray or CT scans). Note: Treatment of the OI that started while on study should be based on local SOC.
- aa. **Post-treatment Follow-up Procedures** – Every 3 months from the last dose of study drug to obtain data regarding changes in efficacy assessments, death or subsequent therapy based on standard of care assessments. Imaging tests to assess disease status will be performed at least once every 6 months or earlier as indicated per standard of care. Any AE that has not returned to baseline or Grade  $\leq 2$  should be followed until it has returned to baseline or better, the event is assessed as stable by the Investigator, the subject is lost to follow up, or the subject withdraws consent. Survival follow-up will continue for up to 3 years after the last subject is enrolled in the study.
- bb. **Response assessment** – Imaging scans, physical examination, bone marrow aspirate/biopsy (if applicable), and laboratory evaluation as appropriate for individual subjects.
- cc. **Response assessment at the EOT/30-Day Safety Follow-up visit** – Perform imaging test (CT scan or PET/CT scan) only if last imaging tests outside the window noted for CT scan or PET-CT.
- dd. **CT Scan** – CT of the neck, chest, abdomen, and pelvis must be obtained at screening (within 6 weeks prior to Cycle 1 Day 1). CT scans must be performed using IV contrast. For subjects who are intolerant to contrast agents, the CT scan will be performed with oral contrast or MRI scans will be used.
- ee. **PET/CT** – FDG-PET scan must be obtained at screening (within 6 weeks prior to Cycle 1 Day 1), as indicated, and to confirm CR/CMR. PET/CT imaging is no longer needed once a CMR has been achieved and a CT scan is an appropriate imaging test.

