### **3.2.4. Progression-Free Survival (PFS)**

PFS is defined as time from first dose of study drug until first disease progression or death from any cause for all groups. Disease progression criteria are defined per Modified Lugano Response Criteria and will be assessed by IRRC and Investigator, independently.

As supportive analysis, PFS2 will be defined as time from first dose of CS after switching until disease progression or death from any cause, and PFS3 will be defined as time from first dose of study drug until disease progression or death from any cause after switching back to the CS. PFS2 and PFS3 are only defined for patients in the ITT IS Population ([Section 4.2](#)) who switched back to the CS.

The censoring rule for PFS will be the same as the ones for primary analysis for DOR ([Table 3](#)), with the exception that subjects with Incomplete or no baseline tumor assessments or no additional follow-up data obtained will be censored at first dose date.

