## 5.3. Missing Data

Missing efficacy data will not be imputed.

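### The SAP's default 28-day baseline has no exception for tumour imaging, yet CT and FDG-PET are accepted up to 6 weeks before first dose; read literally, subjects last scanned on Days -42 to -29 have PFS censored at Day 1

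*SAP*

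**What the plan says.** **Analysis baseline.** SAP 5.2.1 opens with a default: "Unless otherwise specified, baseline is defined as the last non-missing assessment" before first dose, limited to 28 days. The full condition is the "last non-missing assessment prior to the first dose date of study drug and within 28 days of first dose date". It has no sentence on CT, MRI or FDG-PET.

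**Scan window.** Protocol 8.2 states that "PET/CT or CT scans performed within 6 weeks of Cycle 1 Day 1 may be used for screening and eligibility determination", provided the scans meet minimum quality requirements, and gives the aim of sparing subjects repeat tests. For FDG-PET, the protocol's Appendix 1 (footnote ee) says "FDG-PET scan must be obtained at screening (within 6 weeks prior to Cycle 1 Day 1"), and footnote dd sets the same limit for CT. The SAP's Table 1 carries both footnotes over; for CT it reads "CT of the neck, chest, abdomen, and pelvis must be obtained at screening (within 6 weeks prior to Cycle 1 Day 1").

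**PFS rule.** SAP 3.2.4 adds an exception to the usual censoring: "subjects with Incomplete or no baseline tumor assessments or no additional follow-up data obtained will be censored at first dose date".

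**Other rules that bear on this.** SAP 5.2.2 sets change from baseline to missing when the baseline value is missing. SAP 5.3 says "Missing efficacy data will not be imputed". The only tumour-specific baseline rule in the SAP is in 3.2.6 and concerns recapture after progression: "The CT scan at PD will be used as new baseline for assessing disease response to ME-401".

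**The concern.** The SAP's analysis window is shorter than the scan window that the protocol and the SAP's own schedule allow. A subject can be eligible, scanned on time and fully assessed afterwards, and still have no baseline under SAP 5.2.1.

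The main consequence is for PFS. The first-dose censoring in SAP 3.2.4 is written as an exception to the ordinary censoring rules, so on its face it overrides a later observed progression or death. The subject then contributes no follow-up time and no event. SAP Table 4 lists PFS among the selected critical secondary endpoints for the FL primary analysis, and SAP 7.2.4 also summarises it for MZL.

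The other consequences are descriptive. Percentage change in SPD could not be computed, so the subject would be absent from the waterfall plots in SAP 7.1 and 7.2.1. If baseline tumour bulk is derived from that scan, it would also be missing from the baseline table (SAP 6.3) and from the tumour-bulk subgroups of ORR and DOR (SAP 5.5).

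Scans from Days -42 to -29 predate the 28-day screening period, so they are likely to be standard-of-care scans. Their use could differ between sites or with the pace of disease, in which case the loss would not be random. That is plausible, but the documents do not show it.

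**Working it through.** The plan gives no figure to reproduce. The check compares the two windows and follows the rules through.

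**Step 1: the gap between the windows.**
- Permitted scan window (Protocol 8.2; footnotes dd and ee in the protocol's Appendix 1 and in SAP Table 1): 6 × 7 = 42 days before Cycle 1 Day 1.
- Analysis baseline window (SAP 5.2.1): 28 days before first dose.
- Gap: 42 − 28 = 14 days, that is Days -42 to -29, or 14/42 = 33% of the permitted days.

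**Step 2: one subject, two scan dates.** Take a subject with a single pre-dose CT and a progression found by the IRRC during follow-up.

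| Last pre-dose CT | Meets scan window? | Baseline under SAP 5.2.1? | PFS under SAP 3.2.4, read literally | Percentage change in SPD (SAP 5.2.2) |
|---|---|---|---|---|
| Day -20 | Yes | Yes | Event at date of progression | Computed |
| Day -35 | Yes | No | Censored at first dose | Missing |

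The two subjects differ only in scan date, and both dates are allowed.

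**Step 3: is there a fallback?** SAP 5.3 rules out imputing efficacy data. The new-baseline rule in SAP 3.2.6 starts at progression and cannot supply the initial baseline. I found no other SAP text that sets a window for the initial tumour assessment.

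**Step 4: what is not affected.**
- ORR: SAP 7.1 has no exclusion based on baseline, and anyone who does not meet the response criteria counts as a non-responder.
- DOR: it runs from first response (SAP 3.2.2), and Table 2 has no row for missing baseline.

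**Step 5: possible size.** The documents do not report scan dates, so the share *f* of subjects whose latest scan falls in the gap is an assumption. The number affected is N × *f*, with N = 91 for the FL primary efficacy population (SAP 4.3) and N = 32 for MZL (Protocol 11.1).

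| Assumed *f* | FL: 91 × *f* | MZL: 32 × *f* |
|---|---|---|
| 0% | 0 | 0 |
| 5% | 4.6 | 1.6 |
| 10% | 9.1 | 3.2 |
| 20% | 18.2 | 6.4 |
| 33% (14/42) | 30.3 | 10.7 |

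The last row would apply if latest scan dates were spread evenly over the 42 days. It is illustrative only.

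**Step 6: after the fix.** With a 42-day imaging baseline the gap is 42 − 42 = 0 days, and no subject with a compliant scan lacks a baseline because of its date.

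**The case against.** The strongest reply is that the 28-day rule is only a default that yields to anything specified elsewhere. SAP 2.6 sends the reader to Table 1 for assessment timing, and footnotes dd and ee there give imaging its own 6-week window. On that reading the passages already agree and need only a cross-reference. This is a possible reading, but the text does not settle it. The footnotes say when a scan may be obtained, not which scan is the analysis baseline, and neither 5.2.1 nor 3.2.4 cites them.

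The second reply is that Day 1 censoring is inferred. SAP 3.2.4 does not cite 5.2.1 or mention 28 days, and a subject with a CT on Day -35 that the IRRC has read does have a baseline tumour assessment in the ordinary sense. A programmer might simply use the IRRC's baseline. The IRRC methods are in a charter that is not among the documents reviewed. This stands as a limit: the censoring follows from reading two sections together literally. But the SAP does not tell the programmer to use the IRRC's baseline, so two competent programmers could build different PFS datasets from the same plan.

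Three further points stand in full:
- Screening itself is the last 28 days before first dose and the use of older scans is optional, so the number affected could be zero.
- For subjects randomised under Amendment 1, tumour bulk at the 5 cm cut was a stratification factor (SAP 2.5) and so was recorded independently of SAP 5.2.1.
- PFS is summarised by Kaplan-Meier in a single-arm study with no test attached.

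**Conclusion.** The inconsistency is real, and it lies within the SAP as well as between SAP and protocol. Read literally, the SAP discards a permitted baseline scan taken on Days -42 to -29, censors that subject's PFS at first dose whatever happens later, and leaves gaps in the waterfall plots and possibly in the tumour-bulk subgroups. The 14-day gap is exact. The number of subjects is unknown: 0 to about 30 of 91 FL and 0 to about 11 of 32 MZL subjects if the share is anywhere from 0 to 33%.

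A reader might infer more than the documents support:
- *That protocol-compliant subjects in general lack a tumour baseline.* Only those whose latest pre-dose scan falls in the gap are exposed.
- *That a material minority, say 10 to 30%, must be affected.* No document gives a share, and zero is possible.
- *That the trial's main result is at risk.* The primary ORR analysis and overall DOR do not depend on this rule.
- *That bone marrow has the same problem, because Protocol 8.2 accepts biopsies up to 12 weeks old.* SAP 8.4 only lists marrow results, so no analysis is shown to change.

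This should be corrected because it can remove observed events from a secondary endpoint and costs little to put right. It does not call the primary conclusion into question.

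**What to change.** In SAP 5.2.1, add that for tumour imaging (CT, MRI, FDG-PET) baseline is the last evaluable assessment on or before first dose and within 6 weeks of it. In SAP 3.2.4, state that a missing or incomplete baseline tumour assessment is judged against that definition. No change is needed for bone marrow.

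The cost is one sentence and one cross-reference. The window is the one the protocol and SAP Table 1 already allow, so no new data are needed and trial conduct does not change. A count of subjects whose latest pre-dose scan falls on Days -42 to -29, taken from scan dates already held, would show whether the point affects anyone.
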